UNIVERZITNÁ NEMOCNICA MARTIN
[name]
TRANSPLANTAČNO-NEFROLOGICKÉ ODDELENIE
TRANSPLANT-NEPHROLOGY DEPARTMENT

STUDY TITLE

**Physical Performance Assessment in Kidney
Transplant Evaluation Using the Short Physical
Performance Battery (SPPB)**

(FRAIL-KTx)

NCT number:

In Martin, Slovakia 9th JULY 2025

Brief Description

This prospective cohort study investigates physical frailty, assessed by the Short Physical Performance Battery (SPPB), in patients evaluated for kidney transplantation. The study aims to compare SPPB scores before listing, annually during the waiting period, and after transplantation at 6 and 12 months. It also includes a control group of dialysis patients not eligible for transplantation to evaluate differences in physical performance. The goal is to understand how frailty impacts transplant outcomes and patient recovery.

Detailed Description

This longitudinal, prospective study focuses on assessing the role of physical frailty in patients undergoing evaluation for kidney transplantation using the Short Physical Performance Battery (SPPB). The study will enroll adult patients who are being assessed for kidney transplantation, including those who are deemed suitable and placed on the waiting list (Arm A) and those on dialysis who are considered unsuitable for transplant listing (Arm B).

Participants will undergo comprehensive SPPB assessments at baseline, during their evaluation process, and subsequently at annual follow-up intervals. For listed patients, the assessments will be performed upon initial evaluation, then annually while on the waiting list, and at 6 and 12 months following transplantation. For patients ineligible for the transplant list and on dialysis, the SPPB will be recorded at baseline and then annually, allowing cross-sectional comparison and understanding of their physical performance trajectory.

The primary objective is to evaluate changes in physical performance over time with the SPPB score, which ranges from 0 to 12. The scores will be used to categorize participants into frail, pre-frail, or non-frail groups, providing insights into the prevalence and evolution of frailty in this population.

Secondary objectives include comparing the baseline and follow-up SPPB scores between the two arms, correlating physical performance with post-transplant outcomes such as graft function and survival, and identifying potential predictors of frailty that could inform prehabilitation interventions.

This study may inform future strategies to optimize physical function in kidney transplant candidates and improve clinical outcomes through targeted interventions addressing physical frailty.

Study Design:

1. Study Overview

This prospective cohort study aims to assess physical frailty using the Short Physical Performance Battery (SPPB) among patients undergoing kidney transplant evaluation. The study will track physical performance changes before listing, annually for those listed, and at 6 and 12 months post-transplant. A comparison will be made between patients on the transplant waiting list and those on dialysis who are not eligible for listing.

2. Study Design

- **Type:** Longitudinal, prospective cohort study.
- **Duration:** 3-5 years.
- **Participants:** Adult patients undergoing kidney transplant evaluation.

3. Objective

- **Primary Objective:** To assess changes in physical performance using SPPB scores before and after kidney transplantation.
- **Secondary Objective:** To compare SPPB scores between patients on the waiting list and those on dialysis not eligible for the list.

4. Methodology

Inclusion Criteria:

1. Adult patients (≥ 18 years) undergoing evaluation for kidney transplantation.
2. Patients on dialysis.
3. Ability and consent to participate.

Exclusion Criteria:

1. Non-adult patients.
2. Patients unable to provide informed consent.
3. Acute medical conditions prohibiting SPPB assessment.

Study Arms:

- **Arm A:** Patients eligible and listed for kidney transplantation.
- **Arm B:** Dialysis patients not suitable for the waiting list.

SPPB Assessment:

- Measurement of physical performance including:
 - Balance tests (side-by-side, semi-tandem, tandem stands)
 - Gait speed (over a short distance)
 - Repeated chair stands

Data Collection:

TRANSPLANT-NEPHROLOGY DEPARTMENT

- **Baseline:** During initial evaluation for kidney transplantation.
- **Follow-up:** Annually for listed patients; at 6 and 12 months post-transplantation.

5. Statistical Analysis

- **Sample Size:** Estimated 200 patients (100 per arm) to ensure sufficient statistical power.
- **Statistical Tests:**
 - Descriptive statistics for baseline characteristics.
 - Paired t-tests or Wilcoxon signed-rank tests for changes in SPPB scores.
 - Chi-square tests for categorical outcomes.
 - Mixed-effects models to analyze longitudinal SPPB score changes.
 - Kaplan-Meier analysis for survival outcomes related to frailty status.

6. Expected Outcomes

- Characterization of physical performance levels in patients considered for kidney transplantation.
- Identification of changes in physical performance post-transplant.
- Comparison of frailty progression in patients eligible vs. ineligible for the transplant list.

7. Ethical Considerations

- Informed consent will be obtained from all participants.
- Approval from the institutional review board will be secured.

8. Conclusion

This study will provide crucial insights into the implications of physical frailty, as assessed by SPPB, in the context of kidney transplantation. The findings will help in formulating intervention strategies to improve patient outcomes.

Methodology (Detailed)

SPPB Assessment Procedure:

The **Short Physical Performance Battery (SPPB)** evaluates lower extremity function through three components, each scored on a standardized scale. The total SPPB score ranges from **0 to 12**, with higher scores indicating better physical performance and lower frailty levels.

Components and Scoring:

1. Balance Tests (Maximum score: 4 points)

- **Side-by-side Stand:**
 - Held for 10 seconds → 1 point
 - Unable to hold for 10 seconds → 0 points
 - **Semi-tandem Stand:**
 - Held for 10 seconds → 1 point
 - Unable to hold for 10 seconds → 0 points
 - **Tandem Stand:**
 - Held for 10 seconds → 2 points
 - Unable to hold for 10 seconds → 0 points
- Overall balance score:* Sum of these tests, capped at 4 points.

2. Gait Speed (Maximum score: 4 points)

- Time to walk 4 meters (standardized corridor):
 - **> 4.82 seconds:** 0 points
 - **3.00 – 4.82 seconds:** 1 point
 - **< 3.00 seconds:** 2 points

3. Repeated Chair Stands (Maximum score: 4 points)

- Time to rise from a chair 5 times:
 - **> 16.7 seconds:** 0 points
 - **11.2 – 16.7 seconds:** 1 point
 - **< 11.2 seconds:** 2 points

Note: For all components, the best possible score per sub-test is reached if the participant can perform the task within the ideal time or balance parameters.

Scoring Interpretation:

Total Score	Frailty Status
0–6	Frail
7–9	Pre-frail
10–12	Robust/Non-frail (Normal physical performance)

Assessment Protocol:

- **Baseline:** During initial transplant evaluation, clinicians will perform the SPPB following standardized procedures.
- **Follow-up:** The same assessments will be repeated at annual intervals for listed patients and at 6 and 12 months post-transplant.

UNIVERZITNÁ NEMOCNICA MARTIN
[name]
TRANSPLANTAČNO-NEFROLOGICKÉ ODDELENIE

TRANSPLANT-NEPHROLOGY DEPARTMENT

- **Data Recording:** All scores will be documented in the study database, ensuring consistency and reliability.

Additional Notes:

- Assessments should be performed by trained personnel to ensure consistency.
 - Patients will be allowed rest between components to prevent fatigue.
 - Adaptations will be made for patients with mobility aids, if necessary, but these will be noted.
-

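### Annual SPPB in Arm A is conditional on being listed, and the protocol gives no visit or arm rule for a patient removed from the list without a transplant

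*Protocol*

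**What the plan says.** Four arm-specific statements in the Protocol set Arm A's schedule, and all four make the annual visit depend on listing:

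- Detailed Description: "the assessments will be performed upon initial evaluation, then annually while on the waiting list, and at 6 and 12 months following transplantation".
- Section 1, Study Overview: "annually for those listed, and at 6 and 12 months post-transplant".
- Section 4, Data Collection: "Annually for listed patients; at 6 and 12 months post-transplantation".
- Methodology (Detailed), Assessment Protocol: "The same assessments will be repeated at annual intervals for listed patients and at 6 and 12 months post-transplant".

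Arm A itself is defined by listing status (Section 4, Study Arms): "Patients eligible and listed for kidney transplantation". Arm B is defined by unsuitability for the list.

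Two sentences in the Detailed Description point the other way. One is general: "Participants will undergo comprehensive SPPB assessments at baseline, during their evaluation process, and subsequently at annual follow-up intervals". The other is Arm B's schedule: "For patients ineligible for the transplant list and on dialysis, the SPPB will be recorded at baseline and then annually".

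Removal from the list is not mentioned anywhere. The study runs 3 to 5 years, so listing status has time to change. Section 6 expects a "Comparison of frailty progression in patients eligible vs. ineligible for the transplant list", and Section 5 plans mixed-effects models for the longitudinal scores.

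**The concern.** Suitability for listing is plausibly related to physical condition, which is what SPPB measures. If measurement ends when listing ends, the scores most likely to be missing are those of patients who declined. If such a patient is instead counted as Arm B, arm membership itself responds to the outcome. An Arm B patient who improves and is listed later raises the same question in reverse.

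Two aims are exposed: the Detailed Description's objective of change in SPPB over time, as far as it covers the waiting period, and the between-arm comparison of progression in Section 6. An SAP can say how arms are analysed, but it cannot supply scores that were never taken, so the visit rule has to be settled in the protocol.

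**Working it through.** **1. Where a delisted, untransplanted Arm A patient goes under the text**

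| Text followed | Visit after delisting? | Arm |
|---|---|---|
| Arm A schedule (all four statements) | None assigned | Not stated |
| General sentence, Detailed Description | Annual | Not stated |
| Arm B schedule, Detailed Description | Annual, if on dialysis | Moves to Arm B |
| Sections 1 and 4, Assessment Protocol | None assigned to unlisted patients | Not stated |

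Sites could follow different rows and each be within the text. Only the second row keeps measuring without changing the arm, and the sentence after it narrows the schedule for listed patients.

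**2. Simple arithmetic (all inputs assumed)**

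The documents give no delisting rate. Suppose 10% or 20% of Arm A is delisted in an interval with mean SPPB change −2.0, none of it recorded, and the rest change by −0.3.

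- 10%: true mean = 0.9 × (−0.3) + 0.1 × (−2.0) = −0.47. Recorded −0.30. Missed: 0.17 / 0.47 = 36%.
- 20%: true mean = 0.8 × (−0.3) + 0.2 × (−2.0) = −0.64. Recorded −0.30. Missed: 0.34 / 0.64 = 53%.

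Now suppose these patients are counted in Arm B for that interval, with 100 per arm and Arm B's own patients also changing by −0.3.

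- 10 moved: Arm B mean = (100 × (−0.3) + 10 × (−2.0)) / 110 = −0.45. True A minus B = −0.47 − (−0.30) = −0.17; as analysed, −0.30 − (−0.45) = +0.15.
- 20 moved: Arm B mean = (100 × (−0.3) + 20 × (−2.0)) / 120 = −0.58. True A minus B = −0.34; as analysed, −0.30 − (−0.58) = +0.28.

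In this example the arm difference changes sign. It is an unfavourable case by construction: every delisted patient declines steeply and wholly after the last on-list score.

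**3. Simulation over three annual visits (all inputs assumed)**

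Inputs: baseline SPPB mean 9 (SD 2), slope −0.3 per year (SD 0.6), measurement SD 1. The yearly delisting probability at the cohort mean is 5% or 15%, with log-odds 0.3 or 0.6 higher per SPPB point lower. Expected full-cohort change is 3 × (−0.3) = −0.90. Scores are treated as continuous and unbounded. Delisting risk is centred on the cohort mean, so the assumed baseline level does not drive the bias.

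The still-listed results come from 200,000 simulated patients. The mixed model (random intercept and slope) was fitted to 1,200 of them and compared with the full-data change in the same 1,200.

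| Delisting depends on | Yearly risk | Log-odds per point | Listed at year 3 | Change, still listed (all) | Bias | Mixed model (full data) | Bias |
|---|---|---|---|---|---|---|---|
| last observed SPPB | 5% | 0.3 | 84% | −0.87 (−0.90) | 0.03 | −0.96 (−0.94) | −0.02 |
| last observed SPPB | 15% | 0.3 | 61% | −0.80 (−0.90) | 0.10 | −0.76 (−0.80) | 0.04 |
| last observed SPPB | 5% | 0.6 | 79% | −0.82 (−0.90) | 0.08 | −0.93 (−0.91) | −0.02 |
| last observed SPPB | 15% | 0.6 | 58% | −0.74 (−0.90) | 0.16 | −0.79 (−0.87) | 0.08 |
| current unmeasured SPPB | 5% | 0.3 | 83% | −0.79 (−0.90) | 0.11 | −0.86 (−0.95) | 0.09 |
| current unmeasured SPPB | 15% | 0.3 | 59% | −0.61 (−0.89) | 0.28 | −0.69 (−0.90) | 0.21 |
| current unmeasured SPPB | 5% | 0.6 | 77% | −0.64 (−0.90) | 0.26 | −0.69 (−0.89) | 0.20 |
| current unmeasured SPPB | 15% | 0.6 | 56% | −0.44 (−0.91) | 0.47 | −0.43 (−0.89) | 0.46 |

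Positive bias means that the decline looks smaller than it is. With the mixed model the differences are at most 0.08 when delisting follows recorded scores, and 0.09 to 0.46 when it follows unmeasured decline (0.46 / 0.89 = 52% at the extreme). The year-3 mean among those still listed is 8.3 to 9.4, against about 8.1 in everyone, so it is 0.2 to 1.3 points too high.

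The planned 200 patients (100 per arm) come without error rate, power, effect size or SD, so that figure cannot be reproduced. The point does not depend on it.

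**The case against.** A reader might infer that a delisted patient definitely stops being measured, and that the waiting-list course is therefore read only from patients fit enough to stay listed. The documents do not support that. They never say that measurement ends. The general annual sentence carries no listing condition, and a delisted patient on dialysis could fit Arm B's schedule. No reason for delisting is given and none is linked to SPPB. Patients also leave the list by death or by transplantation, and those transplanted are measured again at 6 and 12 months.

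Three further objections have force:

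- The Detailed Description describes the arms as patients are enrolled, and nothing provides for switching. Arm-switching is a possible reading, not a stated rule.
- The planned mixed model uses all scores before delisting. If the last annual score already shows the decline, little bias remains. That the decline always falls after the last score is one scenario only.
- The primary objective in Section 3 concerns change from before to after transplantation. A patient delisted and never transplanted has no post-transplant score to lose. Section 3's secondary objective names patients on the waiting list, so an on-list description is partly what is wanted.

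These objections limit the size and reach of the point. They do not remove it: the specific schedule is conditional on listing in every place it appears, the two sentences that might rescue it lead to different arms or to none, and a decline between annual visits that leads to delisting is a realistic course.

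**Conclusion.** The point holds as a gap that permits outcome-dependent loss or reassignment, not as a demonstrated bias. Annual SPPB in Arm A is tied to listing, and a patient removed without a transplant is given neither a visit nor an arm. The waiting-list trajectory and the eligible-versus-ineligible progression comparison are exposed; the before-and-after-transplant objective is little affected.

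The size cannot be derived from the documents. On assumed inputs it lies between negligible, when delisting depends on recorded SPPB and the mixed model is used, and about half of the true decline, when delisting depends strongly on unmeasured decline and is frequent. The direction in these scenarios is towards making listed patients look more stable. The correction is cheap and worth making before follow-up accumulates.

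**What to change.** Three changes to the protocol:

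1. Assign the arm at the patient's first listing decision and keep it for all arm comparisons, including for an Arm B patient listed later.
2. Replace the listing condition, in all four places, with: annual SPPB from baseline for every Arm A patient not yet transplanted, whether or not still listed, until transplantation, death, withdrawal or study end. The visits at 6 and 12 months after transplantation stay as they are.
3. Record the date and reason of every delisting or late listing, so that the extent of the problem can be reported.

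An additional analysis with current listing status as a time-varying covariate is optional and can be left to the SAP.

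The cost is some protocol wording and one short test per year for each delisted patient. Some of these patients will be harder to reach, may have to be seen at their dialysis unit, or will decline, so some loss will remain. With reasons recorded, it can at least be described.

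### Annual survivor-only SPPB means and frailty proportions can understate progression in the arm with more deaths, because the planned between-arm comparison has no place for death

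*Protocol*

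**What the plan says.** The Detailed Description states that for Arm B "the SPPB will be recorded at baseline and then annually, allowing cross-sectional comparison and understanding of their physical performance trajectory". Of Arm A it says that "the assessments will be performed upon initial evaluation, then annually while on the waiting list, and at 6 and 12 months following transplantation". One secondary objective there is "comparing the baseline and follow-up SPPB scores between the two arms", and section 6 (Expected Outcomes) promises "Comparison of frailty progression in patients eligible vs. ineligible for the transplant list". Section 2 sets the duration at 3–5 years.

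Section 5 (Statistical Analysis) names the tools. Trajectories fall under "Mixed-effects models to analyze longitudinal SPPB score changes". Change between visits is to be tested by "Paired t-tests or Wilcoxon signed-rank tests for changes in SPPB scores". Outcomes that are categories get chi-square tests. Survival is covered by "Kaplan-Meier analysis for survival outcomes related to frailty status".

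The Scoring Interpretation table has three states: frail (0–6), pre-frail (7–9) and robust (10–12). None of these places says how a patient who has died enters an SPPB or frailty comparison. Mortality is not given for either arm.

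**The concern.** Arm B consists of dialysis patients judged unsuitable for transplantation and followed for years, so deaths are to be expected. The planned Kaplan-Meier analysis by frailty status shows that the sponsor expects survival may differ by SPPB category. If it does, the patients lost before each annual visit are disproportionately the low scorers. The mean of those still alive is then held up by the loss of its lowest members, and the proportion classed as frail is held down.

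Where mortality differs between arms, this distortion differs too and does not cancel in the comparison. At stake is the eligible-versus-ineligible comparison of progression: the arm with more deaths can look as if it declined less than it did. Recipients who die before month 12 likewise drop out of a before/after comparison.

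**Working it through.** **What can be taken from the protocol.** The arms (100 each), the annual schedule, the 3–5 year duration, the 0–12 range and the listed methods. There is no plan figure to reproduce on this point. Mortality, slopes and the link between SPPB and death are all assumed below.

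**Step 1: how many remain.** Under constant annual mortality m, the fraction alive at year 3 is about (1 − m)³.
- Arm A at 4%: 0.96³ = 0.88.
- Arm B at 10%, 15% and 20%: 0.90³ = 0.73, 0.85³ = 0.61 and 0.80³ = 0.51.

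Of 100 patients in Arm B, roughly 51–73 would be left to describe the arm's trajectory, against 88 in Arm A.

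**Step 2: the arm comparison at year 3.** Assumptions:
- Arm B: baseline 6.5, slope −0.7 per year, mortality 10–20% per year.
- Arm A: baseline 9, slope −0.4 per year, mortality 4% per year.
- Both arms: baseline SD 2.5, residual SD 1, scores held to 0–12.
- Hazard of death about 15% higher per point lower.
- Slope SD 0.3 or 0.6.

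Without floor and ceiling, the extra decline in B would be 3 × (0.7 − 0.4) = 0.9. Holding scores to 0–12 changes it slightly.

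| Extra decline in B at year 3 | Slope SD 0.3 | Slope SD 0.6 |
|---|---|---|
| True (all followed) | 0.92 | 0.82 |
| Survivors' mean minus baseline mean | 0.35–0.70 | 0.17–0.57 |
| Paired change in survivors | 0.91–0.93 | 0.73–0.79 |
| Mixed model | 0.87–0.91 | 0.75–0.79 |

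The survivor means lose between 0.92 − 0.70 = 0.22 and 0.82 − 0.17 = 0.65 points. Paired change loses at most 0.82 − 0.73 = 0.09, and the mixed model at most 0.82 − 0.75 = 0.07. The proportion of Arm B classed as frail at year 3 is 74–77% with everyone followed and 66–73% among survivors.

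**Step 3: dependence on why patients die.** A second simulation gives both arms the same true 3-year change, −1.5 (baseline 7, between-patient SD 2.0, residual SD 1.0, slope SD 0.6). Except in the first row, the odds of death double per SD worse on the driver. Each cell shows the apparent change at 5% and at 15% annual mortality, with the spurious gap in brackets.

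| Death depends on | Survivors' mean minus baseline | Paired | Mixed model |
|---|---|---|---|
| Nothing related to SPPB | −1.50, −1.49 (0.01) | −1.50, −1.49 (0.01) | −1.53, −1.47 (0.06) |
| Last observed score | −1.27, −0.85 (0.42) | −1.47, −1.39 (0.08) | −1.60, −1.55 (0.05) |
| Current true score | −1.22, −0.72 (0.50) | −1.40, −1.21 (0.19) | −1.39, −1.33 (0.06) |
| Individual slope | −1.32, −0.99 (0.33) | −1.32, −0.98 (0.34) | −1.36, −1.21 (0.15) |

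The mixed-model figures carry simulation noise of about 0.05–0.1. When death is unrelated to SPPB there is no bias beyond that noise. When it is related, the cross-sectional comparison suffers under every mechanism. Paired change suffers seriously only when rates of decline vary and drive death. The mixed model is about unbiased when recorded scores predict death, and drifts when unrecorded decline does.

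**The case against.** - **Handling of death is often left to the SAP, which is not shown.** This stands for missing-data technique, and the mere absence of such a method is not the point here. The protocol itself commits to annual cross-sectional comparison, tests of categorical outcomes and a between-arm comparison of progression. It fixes the outcome states without one for death.
- **The protocol assigns longitudinal change to the mixed model, and an annual comparison of living patients is a legitimate description.** This largely stands. The harm arises only if progression is read from the survivors' means or proportions, which the sentence on Arm B invites by offering cross-sectional comparison and trajectory together.
- **A reader might infer that paired tests and mixed models are equally at fault, or that the bias is certain.** The working does not support either reading. The methods differ widely, and the bias vanishes when deaths are unrelated to SPPB.
- **Death is not ignored.** True: Kaplan-Meier by frailty status is planned, as is correlation of performance with post-transplant survival. Neither is linked to the arm comparison of SPPB.
- **The simulation simplifies Arm A.** Listed patients leave the annual schedule at transplantation, so many may have no year-3 score. The printed component bands also sum to at most 4 + 2 + 2 = 8. As written, an Arm A mean of 9 could not occur and the robust category would be empty. Both limits stand, so the sizes are illustrations on a nominal 0–12 scale.

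**Conclusion.** The point holds for cross-sectional survivor means and frailty proportions, and it is conditional. If low scorers die sooner and mortality is higher in Arm B, these summaries can understate Arm B's progression. Under the assumed 10–20% versus 4% annual mortality, a true extra decline of 0.8–0.9 points at year 3 appears as about 0.2–0.7.

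The protocol gives no mortality, slope or hazard by arm, so neither the size nor the direction of the bias can be read from it. Paired change is much less affected unless individual slopes vary widely and drive death. The mixed model is about unbiased when observed scores predict death. Its remaining issue is one of meaning, because it describes SPPB as if the dead were still measurable.

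It would go too far to say that the whole arm comparison is biased towards no difference. No figure was derived for the before/after comparison in recipients, where the same question arises for deaths before month 12.

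**What to change.** 1. Keep the mixed model as the trajectory comparison. State that it assumes measurability after death, or describe it as function while alive if it is fitted that way.
2. Do not read progression from survivors' annual means or frailty proportions; present them as descriptions of those alive.
3. At each annual visit, report deaths by arm and add a supportive ordinal or rank analysis with the states robust, pre-frail, frail and dead. Do the same at 12 months after transplantation for recipients.
4. Keep patients who leave Arm A's annual schedule at transplantation distinct from deaths.
5. Reconcile two places on which this depends. The follow-up lines under Data Collection and Assessment Protocol name only listed and transplanted patients, while the Detailed Description gives Arm B annual visits. The component score bands do not reach the stated maximum of 12.

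The cost is mainly wording and one extra analysis per visit, since dates of death are needed for Kaplan-Meier anyway. The downside is that the ranked result mixes death and function, so it must be shown beside the mixed model and not replace it.

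### Survival by frailty status is planned only as an unadjusted Kaplan-Meier comparison, which cannot separate frailty from age (or from arm, if arms are pooled), while the stated goal speaks of impact

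*Protocol*

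**What the plan says.** The protocol states its aim on outcomes in two ways. The Brief Description says: "The goal is to understand how frailty impacts transplant outcomes and patient recovery". The Detailed Description lists among its secondary objectives "correlating physical performance with post-transplant outcomes such as graft function and survival". Section 3 (Objective) contains neither; its objectives are SPPB change around transplantation and the comparison of SPPB between arms.

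Section 5 lists five methods. The only one that names frailty status is "Kaplan-Meier analysis for survival outcomes related to frailty status". The others are:
- descriptive statistics for baseline characteristics;
- paired t or Wilcoxon tests for SPPB change;
- "Chi-square tests for categorical outcomes", with no exposure named;
- "Mixed-effects models to analyze longitudinal SPPB score changes", in which SPPB is the outcome.

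No covariate, stratification factor, matching or adjusted survival model is named anywhere in the protocol.

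The design is a prospective cohort. Section 4 admits "Adult patients (≥ 18 years) undergoing evaluation for kidney transplantation" and sets no upper age limit. Arm B is "Dialysis patients not suitable for the waiting list". Section 8 looks ahead to use of the results: "The findings will help in formulating intervention strategies to improve patient outcomes".

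**The concern.** Frailty here is an observed category, not an assigned one. Any factor tied to both low SPPB and death will contribute to the gap between the curves. With entry open to all adults, age is the obvious candidate, even within one arm. If the curves pool both arms, the clinical reasons that made Arm B patients unsuitable for listing are a second candidate.

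None of the other listed methods fills the gap: the chi-square tests are also unadjusted, and the mixed model does not have survival as its outcome.

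At stake is the reading of a secondary result. A gap produced partly or wholly by age could be reported as how frailty affects outcomes, and then cited in support of interventions on frailty.

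**Working it through.** **No figure to reproduce.** The protocol gives no hazards, ages or frailty shares, and no inputs for its 200 patients (100 per arm). Every input below except the 100 per arm is an assumption. Survival is exponential, and frailty has no effect on death within a stratum.

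**1. Age within one arm.** Assume 20% frail, mean death hazard 0.05 per year, 40% of non-frail patients older (pN), a share pF of frail patients older, and older age multiplying the hazard by k. At time zero the apparent hazard ratio is

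HR = (pF·k + 1 − pF) / (pN·k + 1 − pN).

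For pF = 0.6 and k = 2: (1.2 + 0.4) / (0.8 + 0.6) = 1.6 / 1.4 = 1.14. Cox-average values over 3 years:

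| pF | k = 1.5 | k = 2 | k = 3 |
|---|---|---|---|
| 0.4 (same as non-frail) | 1.00 | 1.00 | 1.00 |
| 0.5 | 1.04 | 1.07 | 1.11 |
| 0.6 | 1.08 | 1.14 | 1.23 |
| 0.7 | 1.13 | 1.22 | 1.34 |

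For pF = 0.6, 3-year mortality in frail versus non-frail patients is 14.7% vs 13.7%, 15.2% vs 13.5% and 15.8% vs 13.1%. A steeper gradient is possible: with two equal age strata, 10% and 40% frail, and k = 3, the ratio is about 1.48 over 5 years (reference hazard 0.04).

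**2. Arms, only if pooled (100 + 100).** With frail shares pA, pB and hazards hA, hB:

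HR = [(pA·hA + pB·hB)/(pA + pB)] / [((1−pA)·hA + (1−pB)·hB)/(2 − pA − pB)].

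For shares 0.2 and 0.4 and hazards 0.05 and 0.10: (0.05/0.6) / (0.10/1.4) = 0.0833/0.0714 = 1.17. Shares 0.2 and 0.3 with hazards 0.05 and 0.075 give 1.05. Shares 0.2 and 0.5 with hazards 0.05 and 0.15 give 1.39 over 3 years and 1.40 over 5. Equal shares give 1.00. An extreme case (10% vs 60% frail, fourfold hazard, reference hazard 0.04, 5 years) gives 1.97.

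**3. Sampling error.** The 95% factor either side is exp(1.96/√(d·p·(1−p))), with d deaths and frail share p.
- d = 40: 2.17 at p = 0.2 and 1.97 at p = 0.3.
- d = 14: 3.70 and 3.14.

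With 14 deaths and p = 0.2 the standard error of the log hazard ratio is 1/√2.24 = 0.668. Age biases of 1.08 to 1.23 then lift the rejection rate of a two-sided 5% test to only about 5.2% to 6.1%.

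**4. Events.** Hazards of 0.05 (A) and 0.10 (B) per year; deaths per arm = 100·(1 − exp(−hT)), averaged over T where follow-up varies.

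| Follow-up | Arm A | Arm B | Total |
|---|---|---|---|
| 3 full years | 13.9 | 25.9 | 39.8 |
| uniform 1–3 years | 9.5 | 18.0 | 27.5 |
| uniform 2–5 years | 16.0 | 29.3 | 45.2 |

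Deaths after transplant in Arm A, at transplant rates of 0.15, 0.30 and 0.50 per year and a death hazard of 0.05 throughout, are 2.6, 4.6 and 6.6 over 3 years, and 6.3, 10.3 and 13.6 over 5.

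**5. What the events carry, at 10 per parameter.** Continuous SPPB plus age is 2 parameters, or 20 deaths; an arm stratum uses none. All three totals suffice. The three frailty categories plus age would be 3 parameters, or 30 deaths, and the 27-death case fails. Arm A alone (9 to 16 deaths) carries at most one parameter, and the post-transplant counts do not reach 20.

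**The case against.** The strongest reply is that covariates and adjusted models are ordinary SAP content, and the SAP is not shown. That stands for the missing model: a reader might infer that no adjustment will be made, and the protocol alone does not show this. It does not dispose of the point, because the protocol itself pairs a goal worded as impact with an unadjusted method.

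Second, Kaplan-Meier is a valid description and fits an objective worded as correlation. This also stands, and is why the method should be kept. The other wording of the goal is what it does not serve.

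Third, pooling of the arms is hypothetical. A reader might infer that the plan mixes listed patients with patients unsuitable for listing, but the protocol does not say so. For post-transplant outcomes, which arise only in Arm A, the arm point does not apply. The larger pooled ratios are therefore conditional illustrations.

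Fourth, the assumed age bias is small beside the sampling error and may be nil. That is correct. However, it does not shrink with more patients, and a confidence interval does not show it.

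Fifth, adjustment cannot be supported where the outcome aim lies, after transplant. This is correct too, and limits what the fix can promise.

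Finally, the gait and chair-stand bands in the detailed methodology list at most 2 points each, so the printed maximum total is 4 + 2 + 2 = 8 against a stated 12. The assumed frail shares cannot be tied to that scale. This is a separate inconsistency to be reconciled, and age adjustment does not repair it.

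**Conclusion.** The concern holds in limited form. As written, the protocol relates survival to frailty status by a crude comparison that does not match a goal expressed as impact, and that cannot separate frailty from age. It also cannot separate frailty from unsuitability for listing if the arms are pooled.

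The size is unknown from the documents. Over the main assumed range, the apparent hazard ratio from age within one arm is 1.00 to about 1.34 with no true frailty effect, against a 95% factor of 3.1 to 3.7 either side at 14 deaths.

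A reader might infer that any frailty gap the study reports will be spurious, or that the study's main result is compromised. Neither follows: the bias depends on age differences that the documents do not describe, and the primary objective, change in SPPB, does not use this analysis. This is a cheap improvement on a secondary aim. It should be made, but it is not a fatal flaw.

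**What to change.** Keep Kaplan-Meier as description, drawn within arm. Add to Section 5:

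> *The association of baseline SPPB score (continuous, one parameter) with all-cause death will be estimated with a Cox model adjusted for age and stratified by arm. Post-transplant outcomes will be described in transplanted Arm A patients from the day of transplant, using the last pre-transplant SPPB, without claims of independent effect.*

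In the Brief Description, replace *impacts* with *is associated with*, in line with the correlation wording of the secondary objective.

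The cost is two sentences and one wording change, with standard software and no new assessments. The model assumes one SPPB effect common to both arms and a linear effect on the log hazard. Residual confounding must be acknowledged, since age is the only covariate the expected deaths can carry. If the SAP already contains such a model, only the wording change is needed.
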